#### **6.3 Serious Adverse Event (SAE)**

IMPORTANT NOTE — refer to liver toxicity events defined as an SAE in Section 6.1.2.

SAEs are reported in the following manner:

- All SAEs (occurring after the subject has received first dose of study drug through the 70 days after the last dose of belantamab mafodotin) will be reported within 24 hours of study staff awareness, using OnCore® (entered in the SAE tab) and GSK SAE form. Supporting de-identified documents (e.g., admission and discharge note) will be uploaded to shared site study folder and emailed (see below). An email notice with the SAE or pregnancy PDF report from OnCore® as well as the GSK SAE form (provided by the multisite team) will be sent to the MCW study PI and MCW Multisite Team (via the MCW Multisite Team email) who will report to GSK (MCW will email to [contact]).
- In addition, if the SAE is unexpected and possibly, probably, or definitely related to study drugs, sites must create a reportable event notice with the sIRB, and complete a MedWatch 3500A and send it in an email to the study PI and MCW Multisite Team email.
  - US FDA MedWatch 3500A found here: http://www.fda.gov/Safety/MedWatch/HowToReport/DownloadForms/default.htm
- All grade 4 and 5 SAEs and any other expedited SAE reports to the IRB must also be reported to DSMC within five calendar days of study staff's awareness by the MCW Multisite Team.
- All SAEs will be followed until satisfactory resolution, or until the site investigator deems the event to be chronic. Any significant update/resolution should be updated in OnCore® follow-up SAE report (update the sIRB and MedWatch report, if a SUSAR). The SAE OnCore® PDF follow-up SAE form should be reported in the same manner as the SAE process above.

#### **6.4** Adverse Events Not Meeting SAE Definition

#### **Adverse Events**

Any medical condition that is present at the time that the participant is screened will be considered a baseline condition and captured on the baseline OnCore® CRF form and not reported as an AE (though all SAEs that occur after starting treatment are reported in an expedited manner; see below). All new or worsening AEs that occur after starting study drug until 70 days post last dose of belantamab mafodotin will be tracked and followed until resolution, subject withdraws consent, or is lost to follow-up (including subjects who discontinue early).

Changes in the grade of an AE will be documented in the AE CRF to allow an assessment of the duration of the event at each level of severity. Information to be collected includes event description, time of onset, clinician's assessment of severity, expectedness, relationship to study product (assessed only by those with the training and authority to make a diagnosis), and time of resolution/stabilization of the event.

#### **Adverse Event of Special Interest (AESI)**

An adverse event of special interest (AESI) is an adverse event (serious or non-serious) of scientific and medical concern specific to the sponsor's product or program, for which ongoing monitoring and rapid communication by the investigator to the sponsor may be appropriate. Such events may require further investigation in order to characterize and understand them. AESIs may be added or removed during a study by protocol amendment.

#### Current list of AESIs:

- Elevated serum creatinine (increases from baseline by >0.5 mg/dL).
- Serum creatinine >3.0 mg/dL from baseline OR 3.0-6.0 X ULN.
- Thrombocytopenia.
- Infusion-related reactions.

Short Title: MCW EMBRACE TRIAL Version No.: 3 Version Date: 12/29/2022

- Pneumonitis grade 2.
- Corneal events (severity of corneal events will be graded according to the KVA scale).

All AESIs that meet the definition of an SAE will be reported according to the manner above for SAEs. All AESIs that do not meet the definition of an SAE (or grade 4, see below) must be reported in a routine manner on data forms (which indicate the event is an AESI).

#### **Grade 4 AEs**

Any grade 4 AE that meets the definition of an SAE will be reported according to the manner above for SAEs. A hematological grade 4 AE that does not meet the definition of an SAE will be routinely reported.

Any non-hematological grade 4 AE that does not meet the definition of an SAE will be reported within 24 hours of study staff awareness in the following manner:

- Enter the AE into OnCore® AE CRF.
- Email the MCW Study PI and MCW Multisite Team (via the Multisite Team email; the Multisite Team will notify DSMC coordinator, if required) detailing the following information:
  - o Case/sequence number of the subject.
  - Date of event.
  - o CTCAE term.
  - o CTCAE grade.
  - o Relationship to study drug(s).
  - Expectedness.
  - o Any clinical action taken or planned.

#### 6.5 Unanticipated Problem Involving Risk to Subject or Other (UPIRSO)

The Office for Human Research Protections (OHRP) considers unanticipated problems involving risks to participants or others to include, in general, any incident, experience, or outcome that meet all of the following criteria:

- Unexpected in terms of nature, severity, or frequency given (a) the research procedures that are described in the protocol-related documents, such as the Institutional Review Board (sIRB)approved research protocol and informed consent document; and (b) the characteristics of the participant population being studied.
- Related or possibly related to participation in the research ("possibly related" means there is a reasonable possibility that the incident, experience, or outcome may have been caused by the procedures involved in the research).
- Suggests that the research places participants or others at a greater risk of harm (including physical, psychological, economic, or social harm) than was previously known or recognized.

#### **6.6 DSMC Reporting**

All internal reports to the DSMC and subsequent DSMC review letters will be available to participating sites (e.g., shared site study folder). For those internal events that do not meet the definition of an SAE but are required by the protocol to be reported to the DSMC, the participating site will report according to the protocol.

#### **6.7 Reporting Pregnancy**

#### Male participants with partners who become pregnant:

- Investigator will attempt to collect pregnancy information on any female partner of a male study participant who becomes pregnant while participating in this study and for six months following the last dose of belantamab mafodotin. This applies only to male participants who receive study intervention.
- After obtaining the necessary signed informed consent from the pregnant female partner directly, the investigator will record pregnancy information on the appropriate form and submit it to study PI, MCW Multisite Team, and GSK within 24 hours of learning of the partner's pregnancy.
- Participating sites should report the pregnancy in OnCore® as a grade 3 SAE and complete the pregnancy report form (provided by sponsor as an additional document), and email both PDF reports to the study PI, MCW Multisite Team (via the MCW Multisite Team email), and commercial manufacturers within 24 hours of staff awareness.
- The female partner will also be followed to determine the outcome of the pregnancy. Information on the status of the mother and child will be forwarded to GSK within 24 hours of study staff awareness.
- Generally, follow-up will be no longer than six to eight weeks following the estimated delivery date. Any termination of the pregnancy will be reported regardless of fetal status (presence or absence of anomalies) or indication for procedure.

#### Female participants who become pregnant:

- Investigator will collect pregnancy information on any female participant who becomes pregnant while participating in this study and for four months following the last dose of belantamab mafodotin.
- Information will be recorded and submitted to study PI, MCW Multisite Team, and GSK within 24 hours of learning of a participant's pregnancy.
- Participating sites should report the pregnancy in OnCore® as a grade 3 SAE and complete the pregnancy report form (provided by sponsor as an additional document), and email both PDF reports to the study PI, MCW Multisite Team (via the MCW Multisite Team email), and commercial manufacturers within 24 hours of staff awareness. Participant will be followed to determine the outcome of the pregnancy. The investigator will collect follow-up information on participant and neonate, which will be forwarded to GSK within 24 hours of study staff awareness. Generally, followup will not be required for longer than six to eight weeks beyond the estimated delivery date.
- Any termination of pregnancy will be reported, regardless of fetal status (presence or absence of anomalies) or indication for procedure.
- While pregnancy itself is not considered to be an AE or SAE, any pregnancy complication or elective termination of a pregnancy for medical reasons will be reported as an AE or SAE.
- A spontaneous abortion is always considered to be an SAE and will be reported as such.
- Any SAE occurring as a result of a post-study pregnancy which is considered reasonably related to the study intervention by the investigator, will be reported to study PI, MCW Multisite Team, and GSK within 24 hours of study staff awareness, according to the SAE reporting process above.

#### **6.8 Protocol Deviations and Medication Errors**

Significant deviations are defined, but not limited to, the following:

- Enrolling an ineligible subject.
- Non-compliance: violates federal regulations or institutional policies regarding informed consent or research conduct which impacts subjects' rights, welfare and/or safety or affect the scientific integrity of the project.
- Deviations that have an impact on primary objectives of the study.
- Prohibited medications which pose a safety risk to the patient or integrity of the data.

Planned deviations are defined as follows:

- Any temporary protocol deviation that is anticipated to occur but hasn't occurred yet.
- Sites must follow the sIRB policies regarding acknowledgment prior to deviation initiation.

Significant and/or planned deviations and medication errors are reported in the following manner:

- Participating sites enter the deviation into OnCore® and email the PDF report to the MCW Multisite Team (via the MCW Multisite Team email) within five calendar days of staff awareness.
- Participating sites report to the sIRB.

Any other deviation that is not significant or planned is to be reported in OnCore® in a timely manner (refer to Section 6).

The following actions may occur due to persistent or significant deficiencies:

- Telephone call between the MCW Multisite Team and site staff to discuss resolution or possible prevention of future deficiencies.
- Schedule additional, or short interval, monitoring visits and/or training sessions with the MCW Multisite Team.
- Formal notification to participating site PI of deficit with request for corrective action plan, and/or due date for outstanding items to be completed.
- Warning of potential suspension of participating site accrual until corrective action is completed.
- Suspension of accrual at participating site.
- Participating site accrual closure.

#### 6.9 Staff, Subject, and Product Complaint Reporting

If a complaint is received by anyone on the study staff, it will be addressed on a case-by-case basis. The site PI will be notified of any complaints. Complaints will be reported to the sIRB and MCW PI if required. If the subject has questions about his or her rights as a study subject, wants to report any problems or complaints, obtain information about the study, or offer input, the subject can call the research subject advocate. This information is provided to the subject in their consent.

A product complaint is a verbal, written, or electronic expression that implies dissatisfaction regarding the identity, strength, purity, quality, or stability of the product. The following are examples of product complaint types:

- Labeling Complaints
  - o Damaged or defective label.
  - o Batch number/expiry date issues (for example, not able to read or missing).

- o Directions for use not easy to understand.
- Packaging Complaints
  - o Defective packaging.
  - o Dose difficult to dispense.
- Vial Complaints
  - o Broken, dirty, or cracked vial.
- Stopper Issues
  - o Coring, damaged, or pushed into vial.
- Appearance Complaints
  - o Vials cloudy.
  - o Dissolution difficulty.
  - o Vials contain foreign material.
  - o Dusty capsules.
  - o Capsule or tablet color.
  - o Capsule difficult to swallow.
  - o Drug delivery system complaints.
  - o Leaking after injection.
  - O Dose knob difficult to push.
  - o Pen is jammed.
  - Error codes.
  - o Difficult to attach/detach needle.
  - Unable to set dose.
  - Electronic malfunction.

Study staff who identify a product complaint situation for any study agent should report the complaint within 24 hours of study staff awareness, in the following manner:

- Complete the study-specific product complaint form.
- Email GSK (as relevant), and also the MCW Multisite Team (via the MCW Multisite Team email) the product complaint form and upload it into shared site study folder.
- File the original completed product complaint form in the shadow chart.
- Return product sample, if requested by drug manufacturer, with a copy of the product complaint form.
- Any written, electronic or oral communication that alleges dissatisfaction related to manufactured clinical drug product with regards to its manufacturing, testing, packaging, or shipping, must be reported by the sponsor institution or qualified designee to study PI, MCW Multisite Team, and GSK within one working day of first becoming aware of the possible defect (email of GSK QA at gsk.com). The product and packaging components in question, if available, must be stored in a secure area under specified storage conditions until it is determined whether the product is required to be returned for investigation of the defect. If the product complaint is associated with an SAE, the SAE must be reported separately in accordance with the protocol, and the SAE report should mention the product quality complaint.

Product complaints in and of themselves are not reportable events. If a product complaint results in an SAE, an SAE form should be completed according to the SAE reporting requirements.

Reporting information is collected for:

- A product complaint unrelated to an adverse event.
- A product complaint associated with a serious or non-serious adverse event.

Version Date: 12/29/2022

Submit a product complaint if there is any alleged deficiency with the drug delivery system:

- Complaints can be expressed directly by the subject or by the MCW PI or Study Chair and staff, based on evaluation of the issue.
- The MCW PI or Study Chair should check the box on the product complaint form: "Adverse Event associated with complaint," when he/she suspects the product complaint may have led to the adverse event.

#### 6.10 Subject Withdrawal

The MCW Multisite Team (via the MCW Multisite Team email) must be notified via email within 24 hours of discontinuation of study drugs or study intervention (preferably prior to discontinuation, in case the study PI could recommend an intervention or clarification), describing the nature of the discontinuation. OnCore® subject status updates (off-treatment date and follow-up start date) and discontinuation eCRF must be completed within 24 hours of discontinuation.

#### **6.11 Reporting UPIRSO to Participants**

The MCW Multisite Team, DSMC, drug manufacturers, and/or MCW or sIRBs may make the determination that an event requires reporting to subjects, either verbally/written documentation or reconsent.

#### **6.12 External or Internal Auditing at Participating Sites**

Sites must inform the MCW Multisite Team (via the MCW Multisite Team email) of any other external or internal audit/QA review (outside that performed according to this protocol's monitoring and auditing plans) prior to its occurrence, and send the final findings/report, along with any corrective action plan, to the MCW Multisite Team and MCW PI.

#### 6.13 Known Adverse Events List

Please see the latest version of the belantamab mafodotin investigator's brochure.

#### 7 PHARMACEUTICAL INFORMATION

#### 7.1 Belantamab Mafodotin

#### 7.1.1 Description

	Belantamab mafodotin	
Dosage form:	Lyophilized powder, 100 mg/vial in single-use vial for reconstitution	
Unit dose strengths:	100 mg/vial (Lyophilized powder)	
Route of administration	Delivered as IV solution over at least 30 minutes.	
Dosing instructions:	Reconstitute belantamab mafodotin lyophilized powder 100 mg/vial 2.0 mL of water for injection (WFI); dilute with saline before use.	
Manufacturer/ source of procurement:	GSK/Baxter	

#### **7.1.2 Storage**

Belantamab Mafodotin Solution, 20 mg/mL, 1.5 mL drug product is supplied as a frozen liquid in a 2R glass vial. Detailed instructions for preparation and administration of doses are provided in the site instruction manual. Prepared doses of belantamab mafodotin in the range of 0.2 – 2.0 mg/mL in 0.9% NaCl should be used as soon as possible and no later than 8 hours from the time of dose preparation including administration because the product does not contain an antimicrobial preservative.

The recommended storage condition of belantamab mafodotin Solution, 20 mg/mL, 1.5 mL drug product is -50°C to -15°C, protected from light. The expiry date, where required, is stated on the product label.

#### 7.1.3 Biochemical and Structural Information

GSK2857916 is an afucosylated humanized IgG1 monoclonal antibody conjugated with an average of four maleimidocaproyl monomethyl auristatin F (mcMMAF [SGD-1269]) that binds to BCMA.

#### 7.1.4 Molecular Weight

Theoretical mass of protein containing carbohydrate conjugated with four drug linker molecules are 152.1 kDa (intact mass).

#### 7.1.5 Physical Form

Clear to opalescent; colorless to yellow to brown liquid.

### 7.1.6 Handling and Drug Accountability

Belantamab Mafodotin for Injection, 100 mg drug product is supplied as a lyophilized powder for solution for infusion. Detailed instructions for preparation and administration of doses are provided in the site instruction manual. Prepared doses of belantamab mafodotin in the range of 0.2 – 2.0 mg/mL in 0.9% NaCl should be used as soon as possible and no later than 6 hours from the time of dose preparation including administration because the product does not contain an antimicrobial preservative.

The recommended storage condition is 2-8°C, protected from light. The expiry date, where required, is stated on the product label. Before use, remove the drug product vial(s) from the refrigerator and allow to stand for approximately 10 minutes to reach room temperature (68°F to 77°F [20°C to 25°C]).

Each vial of the drug product is reconstituted with 2.0 mL of sterile WFI before use. Once reconstituted, the drug product solution in vial(s) should be used to prepare the dose as soon as possible. If the reconstituted solution is not used immediately, store the vial(s) refrigerated at 36°F to 46°F (2°C to 8°C) or at room temperature (68°F to 77°F [20°C to 25°C]) for up to 4 hours in the original container. Do not freeze. Discard the reconstituted DP vial(s) if not used to prepare diluted dosing solution within 4 hours.

Visually inspect the reconstituted solution for particulate matter and discoloration. The reconstituted drug product solution in vial should be clear to opalescent, colourless to yellow to brown liquid. Discard the reconstituted vial if extraneous particulate matter other than translucent to white proteinaceous particles is observed.

GSK2857916 (belantamab mafodotin) dose rounding instructions:

Participant's weight in kilograms (kg) should be entered to one decimal place and the total dose (mg) will be calculated to two decimal places.

Example:

```
Total Dose (mg) = 97.2 \text{ kg} * 1.9 \text{ mg/kg}
Total Dose (mg) = 184.68 \text{ mg}
```

The quantity of vials dispensed will depend on the participant's weight and dose level.

For dose preparation, withdraw calculated volume of reconstituted DP from the vial(s) for each dose and add to 250 mL IV bag containing 0.9% sodium chloride. The diluted dosing solution is stable at 0.2 mg/mL to 2 mg/mL in 0.9% sodium chloride for injection for a maximum of 6 hours (including infusion time) when stored at room temperature (68°F to 77°F [20°C to 25°C]).

The diluted dosing solution is compatible with the following contact materials: polyvinylchloride and polyolefin IV bags/administration sets and polyurethane catheter. Filtration is not mandatory, but if using a filter use a 0.2 um polyethersulfone (PES) filter. If a closed system transfer device (CSTD) is used, instructions provided by the manufacturer must be followed to ensure intended dose is delivered. If the diluted solution is not used immediately, it may be stored in a refrigerator 36°F to 46°F (2°C to 8°C) for up to 24 hours prior to administration. If refrigerated, allow the diluted solution to equilibrate to room temperature prior to administration. The diluted solution should be inspected visually for particulate matter and discoloration prior to administration, whenever solution and container permit. The diluted infusion solution should be clear and colorless. Discard if particulate matter is observed.

Density of reconstituted belantamab mafodotin after addition of 2 mL sterile WFI to lyophilized powder (50mg/mL) is 1.0418 g/cm3 at room temperature 68°F to 77°F (20°C to 25°C).

The site PI is fully responsible for the investigational products at the trial site. Dispensing of investigational products will be delegated to site staff. The person responsible for dispensing the investigational products will be accountable for maintaining adequate control of the investigational products and for documenting all transactions with them.

Version Date: 12/29/2022

The site PI, or a responsible party designated by the site PI, will maintain a careful record of the inventory and disposition of all agents. Each participating site PI, or authorized designee, is responsible for maintaining a careful record of inventory and disposition of all investigational agents received at the site. Use of the NCI Drug Accountability Record Form is recommended, but sites may use their own accountability logs per institutional standards. Sites must ensure accountability records capture the same information as the NCI Drug Accountability Record Form and in addition, capture the preparation time. Any used or partially used vials may be destroyed on-site per the institutional standard of practice. Expired vials remaining at the end of the study may be destroyed onsite per institutional standards.

#### 7.1.7 Drug Supply

Provided by funder, drug manufacturer.

Belantamab mafadotin will be provided by GSK through ALMAC, a vendor managing the labeling and shipping of drug. The initial shipment of drug will be initiated by GSK and resupply orders will be the responsibility of each participating site. WebEZ is only used to order drug, it does not require any patient information.

#### 8 STATISTICAL CONSIDERATIONS

8.1 General Description

This phase II study will be conducted using an optimal two-stage design based on the methods of Huang (35). The enrollment target will be 45 subjects, with an interim analysis for futility after 23 patients have been enrolled, and followed for 12 months post diagnosis. Enrollment of new subjects will continue during that period.

The design is based on a modification of a binomial two-stage design that allows incorporation of data from subjects with less than full follow-up at the interim analysis (Huang, 2010). The study will enroll up to 45 subjects with an interim analysis performed when 23 patients have been treated and followed to the 12th month after CAR-T. The futility decision will use the Kaplan-Meier estimate of the 12-month progressionfree conditional survival using the data from the first 23 subjects and any subject who have been enrolled during the follow-up period of the 23rd subject. The study will be stopped for futility, if the one-sided ztest comparing the 12-month progression-free conditional survival to 54% defined by the null hypothesis has a p-value of 0.54 or higher. The study has a 70% probability of stopping for futility if the underlying 12-month conditional PFS equals to the null-hypothesis value of 54%.

If the study is not stopped for futility, study enrollment will continue until 45 subjects are enrolled. The final analysis will be performed when all subjects have been followed to 12 months after CAR-T. The Kaplan-Meier estimate of the 12-month progression-free conditional survival will be compared to 54% using a one-sided z-test at a 5% significance level.

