#### **8.2.2 Primary Hypothesis**

We hypothesize that, with belantamab masodotin maintenance, the 12-month PFS conditional on being progression-free at day +90 will exceed 54%.

The comparison value was selected based on published and preliminary data from the KarMMa2 trial, with three-month PFS of 74%, and 12-month PFS of 40%, resulting in a conditional PFS of 0.4/0.74=0.54. A 5% one-sided type I error rate will be used.

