#### **8.2.3** Sample Size Justification

The sample size was computed using 80% power at a one-sided 5% significance level to detect a significant effect if the conditional PFS exceeds the historical value by 20%, that is 74%. Assuming a 74% three-month PFS, this corresponds to a 12-month PFS of 55%.

The OptInterim R package was used to compute the optimal two-stage design that minimizes the expected sample size, assuming exponential PFS and recruitment of one patient/month during year 1, and two patients/months afterwards. The optimal design recruits a total of 45 subjects, with an interim analysis after 23 subjects have been enrolled, and followed for 12 months post-CAR-T. Recruitment will not be paused during for the interim analysis, and the information from all treated subjects (even those with incomplete

Short Title: MCW EMBRACE TRIAL Version No.: 3 Version Date: 12/29/2022 follow-up) will be used in the interim analysis. This design achieves an 84% power in the hypothesized setting, which exceeds the target due to the discreteness of the design space,

We conducted simulation studies to confirm that the actual study design maintains the target type I error and power under a range of scenarios, including non-exponential survival, up to 10% censoring, and an enrollment window of 1.5 months without additional adjustment of the sample size.

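### The futility cutoff of p ≥ 0.54 gives about a 46% chance of stopping under the null, not the stated 70%; the 0.54 may be a z-value written as a p-value

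*Combined protocol and SAP*

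**What the plan says.** Section 8.1 sets a two-stage design with 45 subjects and one futility look, taken when 23 have been treated and followed to month 12 after CAR-T. On the test itself it says "The futility decision will use the Kaplan-Meier estimate of the 12-month" conditional PFS, compared with 54% by a one-sided z-test. The trial stops if that test "has a p-value of 0.54 or higher. The study has a 70% probability of stopping for futility" if the true conditional PFS is 54%.

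Section 8.2.2 derives the null value ("resulting in a conditional PFS of 0.4/0.74=0.54") and sets the level: "A 5% one-sided type I error rate will be used". Section 8.2.3 takes 74% as the alternative. It assumes exponential PFS and accrual of one patient per month in year 1 and two per month afterwards, does not pause enrollment for the look, and reports "This design achieves an 84% power in the hypothesized setting". It does not restate the futility boundary. The cutoff appears only in Section 8.1.

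**The concern.** The cutoff and the stopping probability stand in adjacent sentences and cannot both be right. A p-value cutoff above 0.5 stops only when the estimate falls below the null value, and under the null that happens less than half the time in large samples. A 70% stopping probability requires a boundary on the other side of the null, at an estimate moderately above 54%.

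This is the trial's only efficacy stopping rule; the monitoring rules in Section 8.2.5 concern toxicity. If the interim z falls between −0.10 and +0.54, the written rule continues the trial and the rule that matches the stated 70% stops it. That interval runs from an estimate slightly below 54% to one moderately above it. If the conflict is found only when the interim data are in hand, the boundary will have to be chosen after the result is known.

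**Working it through.** **Inputs.** From Section 8.1: cutoff p ≥ 0.54, one-sided z-test against 54%, stated null stopping probability 70%, look at 23 subjects followed to month 12 after CAR-T. From Sections 8.2.2 and 8.2.3: null 0.54, alternative 0.74, one-sided 5%, N = 45, exponential PFS, the stated accrual, and use of data from subjects with partial follow-up.

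**1. Large-sample check of the stated 70%.** At the null value z is approximately N(0,1) and the one-sided p-value is 1 − Φ(z), approximately uniform on (0,1).

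- Rule as written: P(p ≥ 0.54) = 1 − 0.54 = 0.46. The equivalent z cutoff is Φ⁻¹(0.46) = −0.100.
- Cutoff needed for 70%: z ≤ Φ⁻¹(0.70) = 0.524, that is p ≥ 0.30.
- 0.54 read as a z cutoff: Φ(0.54) = 0.7054, which is p ≥ 1 − 0.7054 = 0.2946.

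The plan's 70% is not reproduced by the rule as written. It is reproduced, to rounding, by z ≤ 0.54. Under the null, the share of trials falling between the two boundaries is 0.705 − 0.46 = 0.245, about one in four.

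**2. Does the small sample explain the gap?** Exact binomial with p₀ = 0.54, at the two extremes of information (23 subjects only, or all 45):

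| Rule | n = 23 | n = 45 |
|---|---|---|
| p ≥ 0.54 (z ≤ −0.10) | 51.1% | 40.4% |
| z ≤ 0.54 | 67.2% | 74.4% |

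For n = 23 the null expectation is 23 × 0.54 = 12.42 with SD √(23 × 0.54 × 0.46) = 2.39. Twelve event-free patients give z = −0.18, thirteen give 0.24 and fourteen give 0.66. The written rule therefore stops at 12 or fewer, and the z rule at 13 or fewer.

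**3. Does the Kaplan-Meier method explain it?** Simulation with 5,000 trials per scenario: the look when the 23rd subject reaches month 12 after CAR-T, all treated subjects included, left-truncated Kaplan-Meier with Greenwood variance, and z-tests on the plain, log and complementary log-log scales. The exponential scenarios cover treatment-start windows of 0, 1 and 1.5 months, Poisson accrual and 10% censoring. Simulation error is about 0.7 points.

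| Null stopping probability | p ≥ 0.54 | z ≤ 0.54 |
|---|---|---|
| Exponential PFS, all scenarios | 44.0–45.7% | 66.7–69.9% |
| Weibull PFS, shape 0.7 | 41.6–41.8% | 63.5–64.8% |

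No variant of the written rule comes near 70%. The closest is the binomial with n = 23, at 51%.

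**4. Effect on power and type I error.** At the alternative of 74%, simulated stopping is 0.6–2.2% under p ≥ 0.54 and 3.1–6.3% under z ≤ 0.54. Power is 79.9–90.5% and 79.6–89.8% respectively. Within any one scenario and test scale the two cutoffs differ by at most 0.9 points in power and about 0.5 points in type I error. Test scale, entry window and survival shape matter far more than the cutoff: simulated type I error runs from about 3% to 11% across them under either rule.

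**5. Enrollment at the look.** Twelve subjects enter in year 1, so the 23rd enters at month 12 + 11/2 = 17.5. If treatment starts about 3 months after CAR-T, that subject reaches month 12 after CAR-T about 9 months later, at month 26.5. By then 12 + 2 × 14.5 = 41 subjects are enrolled. The simulations average 39 to 40.

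**The case against.** The contradiction itself is not disputed; its weight is. Power and type I error are essentially the same under either cutoff, because the final test governs the trial's conclusion. Enrollment is not paused, so about 40 of 45 subjects are in by the look. Stopping would spare four or five enrollments, and the difference between the rules is worth about one patient on average at the null (0.245 × 4 to 5). Toxicity is monitored separately.

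The z-value explanation is also an inference. The design output is not in the documents, and 0.54 is the null PFS quoted in the same sentence, so a copying slip is possible. In that case the intended cutoff is unknown. The stated 84% power lies inside the simulated range under both rules, so no error in that figure has been shown. Finally, 46% is a large-sample value; the finite-sample range is roughly 40–51%.

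All of this stands, and it limits the consequences. It does not reconcile the two sentences. Stopping could still shorten treatment for subjects already enrolled, and a pre-specified rule that contradicts its own operating characteristic cannot be carried out as designed.

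**Conclusion.** The concern holds. As written, the futility rule stops an inactive regimen about 46% of the time (40–51% across the exact and simulated checks), against a stated 70%. Such a regimen therefore passes the interim about 54% of the time instead of 30%. The gap is 24 points in large samples and about 19 at its smallest.

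The large-sample figure rests only on the p-value being approximately uniform at the null. The simulated figures add the protocol's accrual, a look timed from CAR-T, and treatment starting at or shortly after month 3. That 0.54 is a z cutoff is the explanation that best fits the stated 70%, but it is not established. The 84% power is a figure to re-check, not a shown error. The harm is a misdescribed and ambiguous stopping decision; there is no material loss of power or type I error control.

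**What to change.** Retrieve the stage-1 boundary from the design software output and correct Section 8.1 before the interim data are seen.

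- If the boundary is 0.54 on the z scale, state the rule as stop if z ≤ 0.54, equivalently one-sided p ≥ 0.295, and keep the 70%.
- If p ≥ 0.54 is intended, restate the null stopping probability as about 46%, or as the value that the design simulation gives.
- If the output shows another boundary, state that one with its own probability.

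In each case give the boundary on one scale (or both, consistently), name the scale on which the Kaplan-Meier z-test is computed, and re-run the design code to confirm or restate the 84% in Section 8.2.3. The cost is one or two sentences and a re-run of existing code, with no extra patients.
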